9.3 Monitoring of the study

During the study, an AstraZeneca representative will have regular contacts with the study site, including visits to:

- Provide information and support to the investigator(s).

- Confirm that facilities remain acceptable.
- Confirm that the investigational team is adhering to the protocol, that data are being accurately and timely recorded in the eCRFs, that blood samples are handled in accordance with the Laboratory Manual and that investigational product accountability checks are being performed.
- Perform source data verification (a comparison of the data in the eCRFs with the subject's medical records at the hospital or practice, and other records relevant to the study) including verification of informed consent of participating subjects. This will require direct access to all original records for each subject (eg, clinic charts).
- Ensure withdrawal of informed consent to the use of the subject's blood samples is reported and blood samples are identified and disposed of/destroyed accordingly, and the action is documented, and reported to the subject.

The AstraZeneca representative will be available between visits if the investigator(s) or other staff at the centre needs information and advice about the study conduct.

9.3.1 Source data

Refer to the Clinical Study Agreement (CSA) for location of source data.

<<Japan Specific additional requirements>>

1. Source data are any data generated as a result of the subject's inclusion in the study (including run-in and/or follow up related to the study) and includes all related medical examinations and other records Original data recorded on the eCRFs and regarded as source data are as specified in the Clinical Study Agreement.

9.3.2 Direct access to source data in Japan

The Head of the institution and the Principal Investigator/sub-investigator will cooperate for monitoring and audit by AstraZeneca, and accept inspection by the IRB or regulatory authorities. All study documents such as raw data will be open for direct access to source data at the request of the monitor and the auditor of AstraZeneca, the IRB, or regulatory authorities.

The monitor(s) will verify data from the eCRFs against source data before collecting the eCRFs to ensure accuracy and completeness of documentation, and assure that the Principal Investigator/sub-investigator has submitted the eCRFs to AstraZeneca. If the investigator(s) wishes to amend the collected eCRFs, the monitor will ensure that the Principal Investigator/sub-investigator has documented the amendment in writing (signed and dated) and provided this to AstraZeneca.

9.4 Study agreements

The Principal Investigator at each/the centre should comply with all the terms, conditions, and obligations of the Clinical Study Agreement for this study. In the event of any inconsistency between this Clinical Study Protocol and the Clinical Study Agreement, the terms of Clinical Study Protocol shall prevail with respect to the conduct of the study and the treatment of subjects and in all other respects, not relating to study conduct or treatment of subjects, the terms of the Clinical Study Agreement shall prevail.

Agreements between AstraZeneca and the Principal Investigator should be in place before any study-related procedures can take place, or subjects are enrolled.

The CSA will be between the AstraZeneca and the Principal Investigator.

9.4.1 Archiving of study documents

The Investigator follows the principles outlined in the Clinical Study Agreement (CSA).

<<Japan Specific procedures>>

- (i) **Study files.** AstraZeneca will provide the Principal Investigator with a file in which to organise and retain all study-related documents. All study documents (including letters from AstraZeneca) should be retained in this file by the Principal Investigator. The monitor will regularly check the file to ensure that all relevant documents are retained. The contents of the file may be audited/inspected by AstraZeneca's auditor, regulatory authorities, or IRB.
- (ii) **Period of record retention.** The study site (and the Principal Investigator) will retain the essential documents specified in the ICH GCP (eg, source document such as medical records, contract, signed consent form). Essential documents should be retained at the study site for following completion of the study, or per regulatory obligations if longer, and thereafter destroyed only after agreement with AstraZeneca. However this is not always applied to those that are not preservable such as blood samples. In the event of any inconsistency between the above-mentioned contents and the contract with the study site, the contract shall prevail. These documents should be retained for a longer period however if needed by AstraZeneca, and the specific period and method of retention will be separately discussed between the study site and AstraZeneca. AstraZeneca should notify the head of the study site in writing when the study related records are no longer needed. The records should be managed by a responsible person appointed by the head of the study site.

<<Japan Specific procedures>>

9.4.2 Deviation from the clinical study protocol in Japan

The investigator(s) must not deviate from or make any changes to the protocol without documented agreement between the principal investigator and AstraZeneca K.K. or the IRB approval based on its deliberations. However, this shall not apply to cases where the deviation or change is necessary to avoid an immediate hazard to the patients or for other compelling medical reasons, or where the changes involve only logistical or administrative aspects of the clinical trial (e.g. changes to the organisation/structure of the sponsor, the name/department name of the medical institution, the address or phone number of the medical institution or the sponsor, the job title of the investigator(s), and monitors).

The investigator(s) should document any deviation from the protocol regardless of their reasons. Only when the protocol was not followed in order to avoid an immediate hazard to the patients or for other medically compelling reason, the investigator(s) should prepare and submit the records explaining the reasons thereof to the sponsor, and retain a copy of the records.

The investigator(s) may deviate from or make a change to the protocol without documented agreement between the principal investigator and AstraZeneca K.K. or the IRB approval, only in the event of a medical emergency, e.g. it is only way to avoid an immediate hazard to the patients. In such case, the principal investigator must notify details of the deviation or change, the reason, and a proposed revision in the protocol if required, to AstraZeneca K.K. and the head of the study site and IRB via the head of the study site as soon as possible, in order to obtain their approval. A certificate of approval by the head of the study site as well as AstraZeneca K.K. should be obtained via the head of the study site.

9.5 Study timetable and end of study

Before a patient's enrolment in the study and any study-related procedures are undertaken the following should be fulfilled:

- Signed Clinical Study Protocol and other agreements between AstraZeneca and the principal investigator/Study Site
- Approval of the study by the IRB/IEC
- Approval of the study by the head of study site (**Japan Only**)
- Approval of the study, if applicable, by the regulatory authority

Planned duration of the study

Study period:

Registration period:

The investigator(s) will be notified by representatives of the sponsor when recruitment is complete.

The end of study is defined as the last visit of the last patient undergoing the study, after which no patient will be exposed to study-related activities.

Discontinuation or suspension of the whole study programme

If AstraZeneca decides to prematurely terminate or suspend the study, the principal investigator, sub-investigator, head of the study site for Japan and regulatory authorities must receive written notification of the reasons for the premature termination or suspension.

The principal investigator/sub-investigator will immediately notify the decision to the patients, give appropriate medical treatment, take necessary measures, and record treatment or measures provided on the source documents.

Completion of the study (Japan Only)

Upon terminating the study, the Principal Investigator/sub-investigator will report in writing the completion of the study as well as the summary of the results to the head of the study site in accordance with the institution's rules. The head of the study site, who is informed of the termination by the investigator(s), will provide a written notification of the results to the IRB and AstraZeneca.

10. DATA MANAGEMENT

Data will be entered in the Web Based Data Capture (WBDC) system at the study site. Trained study personnel will be responsible for entering data on the observations, tests and assessments specified in the protocol into the WBDC system and according to the eCRF Instructions. The eCRF Instructions will also guide the study site in performing data entry. Data entered in the WBDC system will be immediately saved to a central database and changes tracked to provide an audit trail. Site personnel will enter the data in the eCRFs. The data will then be Source Data Verified (SDV), reviewed/ queried and updated as needed. The principal investigator will then sign the eCRF electronically. Clean file occurs when all data have been declared clean and signed by the principal investigator. The data will be frozen and then locked to prevent further editing. A copy of the eCRF will be archived at the study site when the study has been locked.

Dictionary coding

Medical coding is done using the most current version of MedDRA and AstraZeneca Drug Dictionary.

Management of external data

Data Management determines the format of the data to be received from external vendors and coordinates the flow of data to an external environment or clinical database (if applicable). Data Management will ensure that the data collection tool will be tested / validated as needed. External data reconciliation will be done with the clinical database as applicable.

Serious Adverse Event (SAE) Reconciliation

SAE Reconciliation Reports are produced and reconciled with Patient Safety database and/or the Investigational Site.

11. EVALUATION AND CALCULATION OF VARIABLES

11.1 Calculation or derivation of efficacy variable(s)

The tumour assessment at screening is regarded as baseline.

11.1.1 Progression Free Survival

The primary outcome variable, PFS, is defined as the proportion of patients who remain progression-free at 24 weeks.

Observation of disease progression is defined by any one of the following:

- Enlargement of the existing lesion or development of a new lesion according to RECIST (Ver.1.1.) (see Appendix D)
- Death of the patient in the absence of progression

11.1.2 Objective tumour response

Responders are defined as those patients with a best objective tumour response of complete response or partial response during the first 24 weeks of therapy (see RECIST criteria in Appendix D). ORR is defined as the proportion of patients who are responders.

Overall response at Week 12 and Week 24 will be assessed according to the RECIST (Ver. 1.1). The response will not need to be confirmed.

Patients without measurable disease at baseline according to RECIST (Ver1.1) will not be evaluated for objective tumour response but will be assessed for disease progression only (see Section 6.3.1).

11.2 Calculation or derivation of safety variable(s)

The laboratory results and vital signs at Visit 2 pre-dose are regarded as baseline.

11.2.1 Laboratory safety measurements and variables

Section 6.4 provides details on how AEs based on laboratory tests will be recorded and reported. Conditions that are considered by the investigator(s) to be unequivocally due to disease progression will not be recorded as AEs.

At screening, absolute values of laboratory safety data will not be databased; confirmation that the values meet the inclusion or exclusion criteria will be recorded in the eCRF. From Day 1 onwards, all laboratory safety data will be databased. Confirmation that samples have been taken will be recorded in the eCRF for all samples; data will be recorded into the eCRF.

11.2.2 Other significant adverse events (OAE)

During the evaluation of the AE data, an AstraZeneca medically qualified expert will review the list of AEs that were not reported as SAEs and DAEs. Based on the expert's judgement,

significant adverse events of particular clinical importance may, after consultation with the Global Patient Safety Physician, be considered OAEs and reported as such in the Clinical Study Report. A similar review of laboratory data and vital sign will be performed for identification of OAEs.

Examples of these are marked haematological and other laboratory abnormalities, and certain events that lead to intervention (other than those already classified as serious), dose reduction or significant additional treatment.

11.3 Calculation or derivation of patient reported outcome variables-NA

11.4 Calculation or derivation of pharmacokinetic variables

The pharmacokinetic (PK) analyses will be performed at Pharmacokinetics Group, Early Phase Development Department, AstraZeneca K.K. The following PK parameters will be determined using standard non-compartmental methods, based on the individual plasma concentration–time profiles of goserelin following the first dose of ZOLADEX 10.8 mg. The actual sampling times will be used for the PK analysis.

- Maximum plasma concentration (C_{\max})
- Time to maximum plasma concentration (T_{\max})
- Area under the plasma concentration – time curve from 0 to time t ($AUC_{(0-t)}$)
- Area under the plasma concentration – time curve from 0 to specifically 12 weeks ($AUC_{(0-12 \text{ weeks})}$)

11.5 Calculation or derivation of pharmacodynamic variable(s)

11.5.1 Calculation or derivation of the relationship between pharmacokinetic and pharmacodynamic variables

Relationship between plasma concentrations of goserelin and E_2 serum concentrations will be assessed in the PK subgroup.

11.5.2 Population analysis of pharmacokinetic/pharmacodynamic variables - NA

11.6 Calculation or derivation of pharmacogenetic variables - NA

11.7 Calculation or derivation of health economic variables -NA

12. STATISTICAL METHODS AND SAMPLE SIZE DETERMINATION

A comprehensive statistical analysis plan (SAP) will be prepared prior to database lock, which will provide a more detailed specification of the analyses to be performed and the outputs to be produced. The sponsor will produce the SAP and perform all statistical analyses. Any

deviations from those analyses presented here and/or in the SAP will be detailed in the CSR. All outputs will be produced using

12.1 Description of analysis sets

Five patient analysis sets will be used in the study as defined in Table 7: the full analysis set (FAS), per protocol set (PPS), safety analysis set, PK subgroup set, and E₂ subgroup set.

Table 7 Definition of analysis sets

Analysis set	Definition
Full analysis set (FAS)	This population comprises all patients randomised to study treatment (regardless of actual treatment(s) received) who had data available for any endpoint post-randomisation. Patients will be included in the analysis according to the treatment to which they were randomised, thus giving an intention to treat analysis.
Per protocol set (PPS)	This population comprises all randomised patients who received at least one dose of study treatment, and who did not significantly violate or deviate from the protocol. Patients will be included in the analysis according to the treatment which they received.
Safety analysis set	This population comprises all randomised patients who received at least one dose of study treatment. Patients will be included in the analysis according to the treatment which they received.
For patients in the PK subgroup:	
PK subgroup set	This population comprises the subgroup of study patients who were randomised to receive and who did receive ZOLADEX 10.8 mg, and who consented to provide samples for PK and additional E ₂ analyses, and for whom data are available for any PK endpoint post-randomisation.
E ₂ subgroup set	This population comprises the subgroup of study patients who were randomised to receive and who did receive ZOLADEX 10.8 mg, and who consented to provide samples for PK and additional E ₂ analyses, and for whom data are available for any E ₂ endpoint post-randomisation.

More detailed rules for allocation of patients to the different analysis sets defined in Table 7 will be given in the SAP.

The primary analysis set for evaluation of the primary and secondary efficacy and PD outcome variables (for the main study) will be the FAS. Supportive analyses will also be done using the PPS.

Evaluations of safety outcome variables will be performed using the safety analysis set.

For analyses in the PK subgroup, PK and E₂ analyses will be performed using the PK subgroup set and E₂ subgroup set, respectively.

12.2 Methods of statistical analyses

Formal statistical hypothesis testing will only be performed on the efficacy and PD outcome variables (main study). All confidence intervals (CIs) will be two-sided, 95% intervals. See Section 12.1 for a description of analysis sets used in each analysis.

Summaries presented will include patient inclusion/exclusion, attendance at study visits, baseline and demographic variables, medical history, prior and concomitant medication, and all efficacy and safety endpoints.

Each table, figure and listing will be created for “Japanese centres only”, “Non-Japanese centres only” and for “All centres”

12.2.1 Analysis of efficacy and pharmacodynamic outcome variables (main study)

12.2.1.1 Primary outcome variables

For PFS, the proportion of patients who are progression-free at 24 weeks will be calculated for each treatment group. Non-inferiority of the 12-weekly ZOLADEX 10.8 mg treatment regimen to the 4-weekly ZOLADEX 3.6 mg regimen will be concluded if the lower limit of the 95% CI for the difference (10.8 mg minus 3.6 mg) is above -17.5%. The CI for this difference will be calculated using the score-based method recommended by Newcombe et al 2000.

The choice of this limit is based on a 75% relative efficacy of the 12-weekly ZOLADEX 10.8 mg treatment to the 4-weekly ZOLADEX 3.6 mg regimen, for which a 24-week progression-free proportion of 70% is anticipated.

In the analysis, a subject whose overall response at Visit 4(Week 24) is missing or NE will be treated as non-progression-free subject. Though the time window for Visit 4 is set as 24 weeks+7days (see Table 2), a tumour assessment performed 25 weeks or later will be handled as the assessment at Visit 4. However, in case that the tumour assessment for Visit 4 is performed 23 weeks or earlier, the overall response at Visit 4 will be handled as missing.

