- To compare the safety and tolerability profile of ZOLADEX 10.8 mg and ZOLADEX 3.6 mg by assessment of adverse events (AEs)
- To assess the pharmacokinetics of goserelin in Japanese and Non Japanese patients except for patients in China in the PK sub-group following administration of ZOLADEX 10.8 mg by measurement of plasma concentrations of goserelin. And to assess the E₂ serum concentration profiles in the PK sub-group.

Study design

This is a multicentre, open label, randomised, parallel group study to compare ZOLADEX 10.8 mg given every 12 weeks with ZOLADEX 3.6 mg given every 4 weeks.

Target subject population

Pre-menopausal female patients with locally advanced or metastatic ER positive breast cancer who are candidates to receive hormonal therapy.

Investigational product (ZOLADEX 10.8 mg)

- ZOLADEX 10.8 mg (goserelin acetate): one subcutaneous depot injection once every 12 weeks (\pm 7 days).
- One oral tamoxifen 20 mg tablet daily.

Comparator (ZOLADEX 3.6 mg), dosage and mode of administration

- ZOLADEX 3.6 mg (goserelin acetate): one subcutaneous depot injection once every 4 weeks (\pm 7 days).
- One oral tamoxifen 20 mg tablet daily.

Duration of treatment

Study medication will be administered from Day 1 until completion of 24 weeks of study treatment or any other criterion for treatment discontinuation are met whichever is sooner.

Outcome variables

Primary outcome variable

- Efficacy

- The primary outcome variable is PFS at 24 weeks. A progression-free patient is defined as a patient for whom neither objective disease progression nor death (due to any cause) has been observed

Secondary outcome variables

- Efficacy/PD
 - ORR at 24 weeks: with response defined as either a complete or partial response based on the RECIST criteria (Ver. 1.1)
 - E₂ serum concentrations at 24 weeks
 - E₂ serum concentration profiles (PK sub-group only)
- Safety
 - AE profile
- PK analysis
 - Plasma concentration–time profile and related PK parameters of goserelin

Statistical methods

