3.1 Overall study design and flow chart

This is a multicentre, open label, randomised, parallel group study to compare ZOLADEX 10.8 mg given every 12 weeks with ZOLADEX 3.6 mg given every 4 weeks.

Target subject population

Pre-menopausal female patients with locally advanced or metastatic ER positive breast cancer. (See Section 4.1 and 4.2 for inclusion and exclusion criteria)

Study medication

‘Study medication’ is a combination of investigational product ‘ZOLADEX 10.8 mg’ or comparator ‘ZOLADEX 3.6 mg’ and study concomitant medication ‘tamoxifen’.

Study period

This study period is composed of screening period and study treatment /assessment period.

Screening period (Visit 1, Day – 21 to Day 0)

- Only eligible patients should be randomised by assessment based on the inclusion criteria and exclusion criteria (See Section 4.1 and 4.2).

- Eligible patients will be randomised 1:1 to receive ZOLADEX 10.8 mg or ZOLADEX 3.6 mg at visit 2.

Treatment/Assessment period

Administration of Investigational product (ZOLADEX 10.8 mg) or comparator (ZOLADEX 3.6 mg) should be started within 1 day after randomisation. Study concomitant medication (Tamoxifen 20 mg) should be started on the same day of or one day after starting the administration of ZOLADEX.

Study medication will be administered from Day 1 until completion of 24 weeks of study treatment or any other criterion for treatment discontinuation are met whichever is sooner. In other words, administration of ZOLADEX 10.8 mg will be continued until Week 12 or any other criterion for treatment discontinuation are met whichever is sooner. Administration of ZOLADEX 3.6 mg will be continued until Week 20 or any other criterion for treatment discontinuation are met whichever is sooner. Administration of tamoxifen will be continued until Week 24 or any other criterion for treatment discontinuation are met whichever is sooner.

Assessment schedule

Study visits to assess efficacy and safety are scheduled at Day 1 (Visit 2), Week 12 (Visit 3), and Week 24 (see Table 2 for study visit windows).

Assessments to identify disease progression will be conducted at each scheduled visit, Week 12 and Week 24. Assessments for progressive disease will also be done between scheduled visits as clinically indicated.

Final assessment of efficacy will be done at the time of disease progression or at Week 24 (Study completion visit) whichever is sooner.

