12.2.5 Interim analysis -NA

12.3 Determination of sample size

In a study by Klijn et al 2001 and the trial 0008, the proportion of patients who had not progressed during the first 6 months (24 weeks) of treatment with the combination of ZOLADEX 3.6 mg and tamoxifen was estimated to be approximately 70%. Assuming the proportion of patients who are progression-free at 24 weeks is 70% in both treatment groups in this study (and therefore that there is no underlying difference between the two treatment regimens), and define the limit of non inferiority as an absolute difference of 17.5% between these two proportions, a sample size of 216 patients (108 per group) ensures that 80% power is achieved to conclude non inferiority with a two-sided 95% CI (or in other words, at the one-sided 2.5% level of statistical significance). The non inferiority limit of 17.5% equates to the 12 weekly ZOLADEX 10.8 mg regimen having at least 75% of the efficacy of the 4 weekly ZOLADEX 3.6 mg regimen.

The study will also collect PK (and additional E₂) data from a subgroup of patients allocated to the ZOLADEX 10.8 mg treatment group. It is planned to have at least 20 patients with evaluable PK data for this subgroup (at least 10 Japanese patients from Japan, and at least 10 Non Japanese patients from non-Japanese countries except for China). The sample size for this subgroup is not based on formal sample size considerations. Recruitment to this subgroup will be on an ongoing basis until the required number of patients with evaluable PK data are enrolled. Patient recruitment to the main study may be increased above the planned 216 evaluable patients in order to ensure 10 Japanese and 10 Non Japanese patients with evaluable PK data.

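### Scoring a missing or non-evaluable Week 24 response as failure can make the non-inferiority test anti-conservative, depending on how missing scans fall between the arms

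*Protocol*

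**What the plan says.** Protocol section 12.2.1.1 compares the proportions progression-free at 24 weeks and concludes non-inferiority if the "lower limit of the 95% CI for the difference (10.8 mg minus 3.6 mg) is above -17.5" per cent. On the interval it says: "The CI for this difference will be calculated using the score-based method". It then fixes how absent data are scored: "a subject whose overall response at Visit 4(Week 24) is missing or NE will be treated as non-progression-free subject". A Visit 4 tumour assessment done at 23 weeks or earlier is also handled as missing, and so becomes a failure. One done at 25 weeks or later is accepted as Visit 4.

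Section 12.3 gives the operating characteristics: "a sample size of 216 patients (108 per group) ensures that 80% power is achieved to conclude non inferiority with a two-sided 95% CI", equivalently "at the one-sided 2.5% level of statistical significance". The margin is explained as 75% of an expected 70% progression-free proportion. Section 12.1 makes the full analysis set (FAS) primary and the per protocol set (PPS) supportive. Section 6.3.1 asks for tumour assessments to go on to Week 24 after treatment stops for reasons other than progression, where possible and except after withdrawal of consent. No expected rate of missing or non-evaluable scans is given, overall or by arm.

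**The concern.** Scoring missing as failure is usually called conservative. That is true when the aim is to show a difference. Here the aim is to exclude a deficit of 17.5 points or more. If some truly progression-free patients in each arm are recorded as failures only because the scan is absent, both proportions fall, and the higher one falls further in absolute terms. The scored difference is then smaller than the real one but is still tested against the full -17.5.

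What is at stake is the trial's only primary conclusion. A 10.8 mg regimen that really is worse by the whole margin could pass more often than the stated one-sided 2.5%. This is a rule the protocol has chosen and written down, not a detail it has left for the SAP.

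**Working it through.** **Inputs.** 108 per arm (section 12.3) with 1:1 allocation (section 3.1); 70% progression-free in both arms (section 12.3); margin 17.5 points and a score-based 95% interval (section 12.2.1.1), taken as the Newcombe hybrid of two Wilson intervals. The missing share is an assumption: 0 to 20%, unrelated to outcome.

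**The plan's own figure.** n per arm = (1.960 + 0.842)² × [0.70 × 0.30 + 0.70 × 0.30] / 0.175² = 7.849 × 0.42 / 0.030625 = 107.6, rounded up to 108, or 216 in total. This reproduces. Exact binomial enumeration of the Newcombe rule at 108 per arm gives power of 81.4%. Its one-sided error is 2.86% at 52.5% against 70% with no missing scans. That 0.4-point excess over 2.5% comes from the interval and discreteness, not from the missing-data rule.

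**Effect of the rule.** Let m be the share of truly progression-free patients with a missing or non-evaluable Week 24 response. Patients who progressed count as failures with or without the scan. The scored proportions are 0.525(1 − m₁₀.₈) and 0.70(1 − m₃.₆), so

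expected scored difference = −0.175 − 0.525 m₁₀.₈ + 0.70 m₃.₆.

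With equal m this is −0.175(1 − m). It equals the margin again when 0.525 m₁₀.₈ = 0.70 m₃.₆, that is, m₁₀.₈ = (4/3) m₃.₆.

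**Error against a true −17.5 points** (exact enumeration over both binomials, 108 per arm):

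| Missing, 10.8 mg | Missing, 3.6 mg | Expected scored difference (points) | One-sided error |
|---|---|---|---|
| 0% | 0% | −17.5 | 2.9% |
| 5% | 5% | −16.6 | 3.8% |
| 10% | 10% | −15.75 | 4.7% |
| 15% | 15% | −14.9 | 5.8% |
| 20% | 20% | −14.0 | 7.4% |
| 5% | 10% | −13.1 | 10.3% |
| 5% | 15% | −9.6 | 22.2% |
| 12% | 10% | −16.8 | 3.3% |
| 10% | 5% | −19.25 | 1.5% |
| 15% | 10% | −18.4 | 1.9% |
| 20% | 10% | −21.0 | 0.6% |

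**Margin rationale.** With 10% missing, the scored comparator rate is 0.70 × 0.90 = 63%. A deficit of 17.5 points from there retains 45.5 / 63 = 72%, not the 75% on which the margin is justified.

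**Comparators.** Dropping missing scans that are missing at random keeps the error at 2.6–2.7% for 5–20% missing. A visit-based life-table estimate gave 2.3–2.6% in simulation under non-informative censoring.

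**The case against.** The best counter-argument is that neither direction nor size can be known from the protocol. The lower rows of the table bear this out: with enough extra missingness on 10.8 mg the rule protects against a false claim. A reader might infer that the arm with six injections will lose more patients, which would push the error up. The schedule does not settle this. Patients on 10.8 mg have fewer dosing contacts before Week 24, which could work the other way. An unconditional statement that the test exceeds 2.5% is therefore not supported.

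Second, missingness may be informative. If those missing are half as likely to be truly progression-free as assumed, equal missingness of 5% and 10% gives 3.4% and 3.8%. If all of them had progressed, missing = failure is correct and the error stays at 2.9%. Leaving them out would then give about 5.4% at 10% against 5% missing (58.3% of 97 against 73.7% of 103). So non-informative censoring is not automatically the safer primary assumption. This stands, and it is why replacing the primary rule is not required.

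Third, if the endpoint means documented progression-free at Week 24, the error at a −17.5-point difference on that scored endpoint is 2.4–2.9%. This is arithmetically right, but the objective in section 2.1 concerns progression-free survival, and the margin was derived from a progression-free rate.

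A reader might also see a contradiction with the synopsis: "A progression-free patient is defined as a patient for whom neither objective disease progression nor death (due to any cause) has been observed". Read literally, an unscanned patient without an observed event would count as a success. But that sentence is a general definition that does not address missing scans, and section 12.2.1.1 supplies the operational rule. It is not a clear conflict.

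Continued scanning after stopping treatment and acceptance of late scans limit the problem. The PPS analysis changes the population, but no other missing-scan rule is stated for it. Randomised patients with no post-randomisation data leave the FAS, so the rule does not reach every absent patient.

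**Conclusion.** The concern holds conditionally. When missing scans unrelated to outcome are similar in the two arms, or commoner on 3.6 mg, the rule pulls a true −17.5-point deficit inside the margin. The increase is modest at 5% equal missingness (about 1 point over the no-missing 2.9%) and material at 10–20%. It is large if the comparator arm loses clearly more scans. Above a ratio of about 4/3 (10.8 mg to 3.6 mg) the rule is conservative.

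These figures assume 70% true progression-free on 3.6 mg, 52.5% on 10.8 mg, outcome-independent missingness and the hybrid-score interval. The missing rates are assumptions, because the protocol states none. The mechanism and the break-even ratio do not depend on the rate chosen. Because the error rate turns on an unknown pattern of missing scans, the primary rule alone cannot guarantee the stated 2.5% level.

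**What to change.** Missing = failure may remain the primary rule. In section 12.2.1.1, pre-specify that a non-inferiority conclusion must also be supported by:

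- an analysis that does not count missing or non-evaluable scans as failures, for example a life-table or Kaplan-Meier difference at 24 weeks on nominal visits, censoring at the last adequate assessment, with its 95% CI compared with −17.5 points;
- an analysis that imputes missing 10.8 mg patients under the non-inferiority null, that is, with a progression-free probability 17.5 points below the comparator.

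Also report the number of missing and non-evaluable Week 24 responses by arm with reasons, including Visit 4 scans set to missing because they were done at 23 weeks or earlier.

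The cost is a short wording change and a little analysis work, with no extra patients or visits. The life-table assumes non-informative censoring, which is why the imputation analysis goes with it.
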